### 11.3 Study Hypotheses

**SVR:** Among subjects who initiate HCV treatment, rate of SVR will be higher in the mDOT vs. PN arm. We hypothesize that SVR rate will be 80% in PN arm.

**Treatment initiation rate:** A higher proportion of patients in the PN arm will initiate treatment compared to the mDOT arm, which is expected to have 60% treatment initiation rate.

**Adherence rate:** Patients in the mDOT arm will have higher adherence rate, compared to the PN arm which is expected to have 80% adherence rate.

**Treatment completion rate:** Patients in the mDOT arm will have higher treatment completion rate, compared to the PN arm, which is expected to have 80% completion rate.

**Detectable resistance:** Patients in the PN arm will have higher resistance rate, compared to the mDOT arm. We hypothesize that the majority (65%) of patients who fail to achieve SVR will develop detectable resistance, yielding an overall 10% resistance rate.

**Reinfection rate:** The hypothesis is that there will be a minimum 5% reinfection rate based on meta-analysis of reinfection rates in patients treated with IFN-based regimens.

## 11.4 Sample Size Determination

Sample size N=300 per arm, or a total of N=600, was determined based on feasibility of recruitment from all sites during the study period. Power analysis for each hypothesis below is conservatively conducted based on a reduced sample size (N= 270 per arm, or N=540 in total) after considering 10% attrition rates. The target power is 80% with a two-sided significance level of 0.05. To this end, minimally detectable effect sizes and widths of 95% confidence intervals were computed with those parameters and the sample size after attrition.

## 11.5 Primary Analytic Principle

The intention-to-treat principle will be used as the primary analytic principle, which pertains more to a real-world situation. That is, once a treatment was randomly assigned to a participant, the participant's treatment identity will not change in the analysis even if s/he changes to the other model of care during the trial period or did not take the assigned treatment. Other analytic strategies such as per protocol or as-treated analyses will also be applied to examine robustness of effectiveness of mDOT vs. PN.

## 11.6 Preliminary Data Analysis

First, the distributions of all variables will be examined using graphical or descriptive statistics to identify any values out of range. When identified, out of range values will be found in the original record, compared and corrected if needed. Second, although by the stratified randomization design, each arm will equally be distributed across city, clinical site (OTP and CHC) and stage of liver disease (cirrhosis vs. no cirrhosis), the

success of randomization will be checked as a way of checking key assumptions by comparing the PN and mDOT groups on key variables, such as age, gender, ethnicity, race, viral load, subtype, psychiatric history, drug use type, and social support. Continuous variables will be compared between arms using the t-tests or Mann-Whitney tests, and categorical variables will be compared using chi-square or Fisher's exact tests.

Variables that are not equally distributed, albeit expected to be rare, will be included in multivariate models to control for their potential confounding effects. When necessary, normal assumptions will be checked for continuous variables by applying a formal Kolmogorov-Smirnov test, and if violated, Box-Cox transformations will be considered. All preliminary statistical analysis and beyond will be conducted using SAS v9.3.

## 11.7 Missing data analysis

In order to not compromise internal or external validity of our study results, every effort will be made to minimize missing data that could occur due to missed visits or subject attrition. A maximum 10% subject attrition rate is anticipated during the first 24-week intervention period considering a real-world situation that withstands a tight control. However, the missing outcome data rates will depend on the outcome definition whereas most analyses will use baseline characteristics as covariates that will thus have negligible missing data rate.

The primary analysis will be based on available data without missing data imputation; however, we will conduct variety of missing data imputation methods for sensitivity analyses. Depending on the clinical nature of outcome, worst scenario imputation or, if deemed more relevant, mean imputation methods will be considered. In addition, fully specific conditional specification multiple imputation methods will also be applied, which are applicable to non-ignorable missing data.

Characteristics of patients who are lost to follow-up will be compared to those that remain in the study to assess the degree of any selection bias due to attrition, and the analysis results of the different types of imputed missing data will be compared to the primary analysis results. In particular, variability of the coefficients of primary predictors across the different imputation methods will be assessed to evaluate robustness of the findings. If the changes in the coefficients are greater than 15% from those of the primary analysis, we will limit the generalizability, internal and external validity of our findings, which we nevertheless do not believe will occur if attrition rates are less than 25%.

## 11.8 Heterogeneity of mDOT or PN effects

The mDOT or PN effects depending on outcome (see Aim 1 hypotheses) will be assessed for each subgroup stratified various factors (e.g., clinic setting, demographic, or clinical), which are specified below, and will be compared across the subgroup strata. Forest plots will be produced to show graphically the differences or contrasts in effect sizes across all subgroups. Formal tests will follow via testing significance of pertinent interaction terms with the mDOT or PN arm indicator in statistical models.

## 11.9 Mediated mDOT or PN effects

Mediator analysis will be conducted to identify potential mediators between mDOT/PN effect and each of the five outcomes. A mediator will be a variable whose value changes or occurs between the baseline and the end of the study; for example, reduced stigma and shame, extent of peer support, changes in social support, and increased self-efficacy. The potential mediating effects will be assessed by differences in mDOT or PN effect sizes depending on outcome between with and without a potential mediator variable in statistical models. Their significance will be tested following the Baron and Kenny mediation test principle.

## 11.10 Analytic plan for Primary and Secondary outcomes: SVR, Treatment initiation rate, Adherence rate, and Treatment completion rate

### Study Hypotheses:

**SVR:** Among subjects who initiate HCV treatment, rate of SVR will be higher in the mDOT vs. PN arm. We hypothesize that SVR rate will be 80% in PN arm.

**Treatment initiation rate:** A higher proportion of patients in the PN arm will initiate treatment compared to the mDOT arm, which is expected to have 60% treatment initiation rate.

**Adherence rate:** Patients in the mDOT arm will have higher adherence rate, compared to the PN arm which is expected to have 80% adherence rate.

**Treatment completion rate.** Patients in the mDOT arm will have higher treatment completion rate, compared to the PN arm, which is expected to have 80% completion rate.

### Statistical Model

Multivariable logistic regressions will be applied to test the overall effectiveness of mDOT or PN on the five binary outcomes (success vs. failure) with the SVR rate as the primary outcome. The arm indicator will be the predictor for each outcome. With respect to adherence outcome in particular, repeatedly measured adherence will be analyzed (using 6 post-baseline time points and adherence as a continuous measure) applying a mixed effects linear model to test if the two arms are significantly different. This model accounts for within-subject longitudinal outcome correlation by taking the subject-level intercept as random. All models will include potential confounding variables that are significantly different between the two arms; the sites will be included as a covariate as well. Likewise, mixed effects logistic regression will also be applied to test the significance of PN and DOT on repeatedly-measured undetectable HCV VL throughout the intervention period, adjusting for substance use in addition to other confounding variables. Changes in illicit drug use will be analyzed using urine toxicology data from each visit, counting the “person-month” as a unit of analysis, and analyzing the percentage of person-months that are positive for use of illicit drugs during the study period using a t-test or Mann-Whitney test.

### **Power analysis: Minimally detectable effect sizes**

**SVR:** Considering the base 80% SVR rate of in PN arm, a minimum of 9% difference between the two arms will be detected (i.e., 89% vs. 80%, Odds Ratio (OR)=2.1) in a multivariable logistic regression model in which confounding variables will explain 10% of variation in the predictor variable. This study posits that a >9% difference in SVR between the PN and mDOT groups will be clinically significant based on studies that showed that SVR in treatment naive patients was >90% [14].

Mixed effects logistic regression models for the undetectable HCV load will be able to detect even smaller percent point difference since they will utilize repeated measures for each subject no matter how large within-subject outcome correlations will be.

**Treatment initiation rate:** With anticipated 60% treatment initiation rate in the mDOT arm, a minimum of 7% difference will be detectable (i.e., 60% vs. 67%, OR=0.74) in any outcome in a multivariable logistic regression model in which confounding variables will explain 10% of variation in the predictor variable. Note that sample size for this analysis will be N=1000, the total number of randomized participants.

**Adherence rate:** With expected 80% adherence rate in the PN arm, a minimum of 9% difference in adherence rates between the 2 arms will be detectable (i.e., 89% vs. 80%, OR=2.1) in a multivariable logistic regression model. Per the repeatedly measured continuous adherence percentage outcome, mixed effects linear models will be able to detect standardized effect sizes (mean difference divided by a pooled Standard

Deviation (SD)) greater than 0.2 irrespective of magnitudes of within-subject outcome correlations over time. In a previous DOT study, a standardized effect size of mDOT vs. TAU was estimated to be 0.6.

**Treatment completion rate.** Under the expected 80% completion rate in the PN arm, a minimum of 9% difference in completion rates between the two arms will be detectable (i.e., 89% (mDOT) vs. 80% (PN), OR=2.1).

### **Subgroup Heterogeneity Analyses**

To assess heterogeneity of mDOT or PN effects, additional analyses will be conducted to evaluate whether the mDOT effect varies by variety of subgroups stratified by the following characteristics: OTP (50%) vs. CHC (50%); Males (70%) vs. Females (30%); Patients using illicit drugs during treatment (65%) vs. those not using illicit drugs (35%); HIV/HCV coinfected (28%) vs. HCV mono-infected (72%); Cirrhosis (21%) vs. non-cirrhosis (79%); African American / Latino (41%) vs. Caucasian (59%); Marginally housed (26%) vs. stably housed (74%); Comorbid mental illness (55%) vs. no mental illness (45%); and Peer-support (70%) vs. no peer-support (30%). Initially, subgroups will be defined based on the above factors and estimates of treatment effect will be obtained separately in each subgroup using the methods described above. The significance of any heterogeneous mDOT or PN effects across these factors will be formally tested by testing significance of corresponding interaction terms with the mDOT or PN arm indicator. In addition, we will also conduct within-arm subgroup analyses to identify factors that are associated with outcomes within arms. For example, one test would be if increased social support will be associated with higher treatment initiation within the PN arm.

**Power analysis for subgroup analysis:** For the subgroup analysis, the minimally detectable effect size will depend on the sample size of subgroups. However, assuming that a subgroup has 50% of the total sample, i.e., N=270, and that a base outcome rate is 80% (e.g., SVR), then  $\geq 12\%$  difference will be detected using a Chi-square test. The minimally detectable standardized effect size for continuous outcome will be 0.3. This power analysis also applies to detect binary or continuous factors associated with outcome from within-arm subgroups analyses since the sample size of each arm will be N=270 after attritions. For the subgroups with smaller sample size, the minimally detectable effects sizes, binary or continuous, will be larger. For example, for some of our subgroups will be as small as 20% (or, N= 108) of the sample (e.g. HIV/HCV coinfected), minimum effect sizes are larger at  $\geq 17\%$  for SVR and 0.5 standardized effect size for continuous variables.

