## 5.4 Randomization

Up to 1000 patients will be recruited, with patients randomized to PN or mDOT in a 1:1 ratio (500 subjects in each group) in variable block sizes of 2-6 via central, computer-generated randomization provided by the UNM Statistical and Data Coordinating Center (SDCC). Randomization will occur in blocks to ensure comparison groups of approximately equal size. Given that the intervention will not be blinded, block size will vary to prevent anticipation of treatment arm assignment.

Two special randomization strategies (stratification and blocking) will be used to avert imbalances in prognostic factors or treatment settings, and to ensure comparison groups of approximately equal size. Participants will be stratified by 3 factors: city, OTP vs. community health center and stage of liver disease (cirrhosis v. no cirrhosis).

In addition, adaptive re-weighting of random allocation in a pseudo urn randomization fashion will be made when N~300 has been enrolled to balance the sample size between mDOT and PN arms. Specifically, as we hypothesize that number of randomized subjects who will initiate treatment will be larger in the PN arm, unbalancing between arms is likely to occur during the course of the study. Of note, therefore, a randomized subject will not necessarily be a clinical treatment subject but will be included in the comparison of treatment initiation.

To adjust for this potential unbalance, we will adjust randomization based on observed allocation ratio at the middle of trial if the overall allocation difference is greater than 5% (i.e., <47.5% vs. 52.5%).

Storage and dispensing of random allocation codes will be made in a centralized fashion. The UNM SDCC will generate and store the codes for all sites and types of clinics, and will be embedded into the Research and Electronic Data Capture (REDCap) data management system in the backend so that the identification of a treatment assignment will be ready and immediate without contacting the coordinating center when requested through the REDCap electronic request form by a responsible research staff at the sites whenever a new eligible participant is enrolled. The UNM SDCC will also be responsible for conducting re-weighted randomization, if necessary, at the middle of the trial.

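### The protocol's continuous-outcome detectable effects for subgroups (0.3 SD at N=270, 0.5 SD at N=108) give about 69% and 73% power, not 80%, with equal groups and one measurement per subject (minor)

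*Protocol*

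**What the plan says.** Protocol section 11.4 fixes the criterion for the power statements that follow: "The target power is 80% with a two-sided significance level of 0.05". It applies this to a "reduced sample size (N= 270 per arm, or N=540 in total) after considering 10% attrition rates", so attrition has already been taken out.

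The subgroup power paragraph in section 11.10 first takes half the sample, "assuming that a subgroup has 50% of the total sample, i.e., N=270", and gives a 12-point difference for a binary outcome with a base rate of 80%. It then adds: "The minimally detectable standardized effect size for continuous outcome will be 0.3". The same figures are said to cover factors examined within one arm, because each arm also has 270. For the smaller case, "for some of our subgroups will be as small as 20% (or, N= 108) of the sample", the detectable effects are 17 points for SVR and "0.5 standardized effect size for continuous variables".

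The paragraph gives no formula for the two continuous figures. It also states no number of measurements, no within-subject correlation and no rounding convention. Earlier in section 11.10 a standardized effect is defined as the mean difference over the pooled SD.

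**The concern.** A smallest detectable effect is a claim about power: at that effect, the test succeeds with at least the target probability. If the figure is too small, the claim fails. Here the two continuous figures are below what subgroups of 270 and 108 support at 80% power in a plain two-group comparison, while the binary figures in the same paragraph are about right. A reader who relied on the continuous figures would expect a 20% chance of missing a true 0.3 SD difference in a half-sample subgroup, when the chance is about 31%.

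**Working it through.** **Inputs**
- Power 80%, two-sided 0.05 (Protocol 11.4): 1.960 + 0.842 = 2.802.
- Subgroup sizes 270 and 108 after attrition (Protocol 11.10).
- 1:1 randomization (Protocol 5.4), assumed to hold within subgroups: 135 and 54 per group.
- Effect in pooled-SD units (Protocol 11.10), so SD = 1.
- Assumption: one measurement per subject.

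**The paragraph's binary figures reproduce.** Power = Φ{[d − 1.960·√(2·p̄(1−p̄)/n)] / √([p1(1−p1)+p2(1−p2)]/n)}, where d = p2 − p1 and p̄ is the mean of the two rates.
- 80% v. 92%, n = 135: (0.12 − 1.960 × 0.0422)/0.0416 = 0.895, power 81.5%.
- 80% v. 97%, n = 54: (0.17 − 1.960 × 0.0614)/0.0592 = 0.839, power 79.9%.

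So the paragraph's group sizes, two-sided level and 80% target are the ones used here.

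**The continuous figures do not.** Detectable effect = 2.802 × √(2/n).
- n = 135: 2.802 × 0.1217 = 0.341 SD (0.342 by noncentral t). Stated: 0.3.
- n = 54: 2.802 × 0.1925 = 0.539 SD (0.544 by noncentral t). Stated: 0.5.

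Power at the stated effects = Φ(δ/√(2/n) − 1.960):
- 0.3 SD, n = 135: Φ(2.465 − 1.960) = 69.3% (69.0% by t).
- 0.5 SD, n = 54: Φ(2.598 − 1.960) = 73.8% (73.1% by t).

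To detect exactly 0.3 SD takes 175 to 176 per group (350 to 352 in total, not 270). Exactly 0.5 SD takes 63 to 64 per group (126 to 128, not 108).

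**Other readings** (normal approximation)

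| Reading | Power at 0.3 SD | Power at 0.5 SD |
|---|---|---|
| As above | 69.3% | 73.8% |
| Before attrition (N = 300, 120) | 73.8% | 78.2% |
| Covariates explain 10% of the predictor's variation | 64.7% | 69.3% |
| One-sided 0.05 | 79.4% | 83.0% |

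Only the one-sided reading comes close to both figures, and section 11.4 rules it out.

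**Repeated measures.** With m equally correlated measures (correlation ρ), the variance is multiplied by (1 + (m−1)ρ)/m. The stated effects reach 80% power if this factor is at most (0.3/0.341)² = 0.774 and (0.5/0.539)² = 0.860. For m = 6 that means ρ up to (6 × 0.774 − 1)/5 = 0.73 and (6 × 0.860 − 1)/5 = 0.83.

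**Within-arm factors.** With 270 in an arm split unequally, the detectable effect is 2.802 × √(1/n1 + 1/n2). Using splits that section 11.10 lists:
- 30/70 (sex, peer support; 81 v. 189): 0.37 SD. Power at 0.3 SD is 62%.
- 26/74 (housing; 70.2 v. 199.8): 0.39 SD. Power 58%.
- 21/79 (cirrhosis; 56.7 v. 213.3): 0.42 SD. Power 52%.

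**The case against.** The strongest objection is that the single-measure model is not the protocol's only one. Section 11.10 says subgroup effects will be estimated with the methods already described, and for continuous adherence that is a mixed linear model over six post-baseline time points. The paragraph names a chi-square test for the binary figure and no test for the continuous one. With six measures and a correlation below the limits shown, 0.3 and 0.5 SD would be detectable at 80% power. This stands to the extent that 69% and 73% depend on an assumption, which must be stated. A reader might infer that they are fixed properties of the design, and the documents do not support that. Three things still make the single measure the right basis. No correlation is given, the figures are worded for continuous outcomes in general, and the whole-sample adherence figure of 0.2 SD is said to hold whatever the correlation. That must include the limiting case, which is equivalent to one measure.

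The second objection is that 0.34 and 0.54 round to 0.3 and 0.5, so this may be only a matter of reporting precision. That is plausible, and the binary figures suggest a sound underlying method. But it is an inference, since no unrounded value is shown. It would explain the numbers without making them correct, because rounding a smallest detectable effect downwards takes it below the power target.

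Third, a reader might infer that null subgroup results will be over-interpreted. No section says that results will be read against these figures. SAP section 6.2.2 reports odds ratios with confidence intervals alongside tests for the SVR subgroups, and SAP section 6.3 gives subgroup power for SVR only.

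**Conclusion.** Wrong as written, and minor. Under equal groups, one measurement per subject and two-sided 0.05, the stated effects have about 69% and 73% power, which is 11 and 7 percentage points below target. The correct values are 0.34 and 0.54 SD, so the plan understates them by about 12% and 7%. For within-arm factors with unequal splits the shortfall is larger.

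A reader might infer that the trial itself is underpowered. The documents do not support that: section 11.4 says the sample size was set by recruitment feasibility, and neither it nor the primary SVR analysis depends on these figures.

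**What to change.** In the subgroup power paragraph of Protocol section 11.10, replace 0.3 with 0.34 SD and 0.5 with 0.54 SD, and state that both assume equal groups and a single measurement. Alternatively, keep figures based on repeated measures, but give the number of measures and the within-subject correlation they rely on. Add a sentence that within-arm factors with unequal splits need larger effects, for example about 0.37 SD at 30/70 and 0.42 SD at 21/79 with 270 in the arm.

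The whole-sample 0.2 SD for adherence (Protocol 11.10, repeated in SAP 8.4.3) should be checked in the same edit. On the single-measure basis, 270 per arm needs 2.802 × √(2/270) = 0.24 SD.

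The cost is a few words and slightly less favourable numbers. Design, sample size and analysis do not change.

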## 11.11 Analytic plan for Resistance and Reinfection Rates

### Study Hypotheses:

**Detectable resistance:** Patients in the PN arm will have higher resistance rate, compared to the mDOT arm. We hypothesize that the majority (65%) of patients who fail to achieve SVR will develop detectable resistance, yielding an overall 10% resistance rate.

**Reinfection rate:** The hypothesis is that there will be a minimum 5% reinfection rate based on meta-analysis of reinfection rates in patients treated with IFN-based regimens.

### Statistical Model

The precision of proportion of participants who develop resistance or reinfection will be determined with 95% confidence intervals (CIs) calculated using exact binomial methods. To identify factors associated with resistance or reinfection, we will conduct bivariate analysis using (exact) logistic regressions for both continuous and dummy-coded categorical variables. A series of bivariate analyses will be followed by a multivariable logistic regression that includes all factors significant in the bivariate analysis at a two-sided 0.05 significance level. All analyses will be separately conducted for each of resistance and reinfection outcomes. For the examination of association between resistance and adherence in particular, a multivariable logistic regression will also be applied in which overall adherence will be the primary predictor in the presence of other factors identified in the bivariate logistic regression analysis. In all multivariable analysis, the mDOT arm indicator will be included for adjusting purpose.

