### **HCV reinfection among PWID**

Reinfection is a potential problem and a barrier to treatment among PWID [23]. Data collected to date, principally in PWID who have received interferon-based treatments, show reinfection is low: 5.2/100 person years (py) for those who report injection drug use after treatment, and less (3.2/100 py) for those who do not report ongoing injection drug use [39, 40]. However, recent reports have noted higher rates of reinfection after interferon-based treatments in prisoners (8/100 py), HIV/HCV Men who have Sex with Men (MSM) (24/100 py), and PWID who relapse to drug use with longer follow-up (30/100 py). [41, 42]

Prospective studies assessing HCV reinfection PWID who spontaneously cleared infection [43, 44] show that to accurately capture reinfection events, genotyping and viral sequencing is necessary to distinguish reinfection from intercalation. Without these tests, estimates of reinfection incidence were significantly overestimated. Testing interval also has an impact on detection of reinfection. In PWID who clear infection spontaneously, testing intervals less frequent than every three months resulted in substantial (by up to 66%) underestimation of reinfection rate [45]. A caveat here is that these estimates are from patients who spontaneously clear the virus, and who have

been shown to have a high likelihood of re-clearance of subsequent infections [44, 46, 47], and immunological responses to reinfection may differ in those with treatment induced clearance. Systematic testing (every 3 months after SVR12 in our proposed study) to assess the presence of HCV RNA will be essential to accurately determine reinfection events. There is little to no data on reinfection rates in the era of DAAs.

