### 3 Study Objectives

#### 3.1 Primary Objective

To determine whether SVR-12 rates are higher among those randomized to mDOT compared to those randomized to PN, among PWID treated for HCV at OTPs and community health centers.

#### 3.2 Secondary Objective 1

To examine the following outcomes overall and by randomization arm (mDOT compared to PN) among PWID treated at OTPs and community health centers:

- (i) Treatment initiation: whether a higher proportion of participants in the PN arm initiate treatment compared to mDOT arm;
- (ii) Adherence ( $\geq 80\%$  of prescribed medication taken): whether a higher proportion of those in the mDOT arm are adherent compared to PN arm;
- (iii) Treatment completion (finishing 100% of prescribed 12-week course): whether a higher proportion of participants in the mDOT arm complete treatment compared to PN arm;
- (iv) Drug resistance: whether the proportion who develop drug resistance is higher in the PN arm compared to mDOT arm;
- (v) Reinfection: whether (a) rate (incidence), and the (b) proportion who become reinfected with HCV is higher in the PN arm compared to mDOT arm;

Comparisons will be performed to determine the proportion of subjects in each arm who: a) initiate treatment; b) adhere to antiviral treatment; c) complete antiviral treatment; d) attain SVR (cure); e) develop drug resistance; f) reinfection. We will also conduct time to event analyses to examine drug resistance and reinfection outcomes. Subgroup analyses will be performed to assess differences in outcomes among those randomized to PN vs. mDOT in specific sub-populations.

#### 3.3 Secondary Objective 2

To examine factors associated with key study outcomes (treatment initiation, adherence, SVR, drug resistance and HCV reinfection) using quantitative and qualitative methods.

Quantitative methods: We will examine associations between psychosocial factors such as homelessness, co-morbid mental illness, poor social support, and high

levels of shame and stigma, with key study outcomes described above. It is hypothesized that these psychosocial variables are associated with lower rates of adherence and SVR in the PN arm, but not the mDOT arm; and associated with lower rates of treatment initiation in the mDOT arm, but not the PN arm.

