#### **8.6.9 Visit 13: week 120, ± 14 days**

Research staff will assess for factors of interest by administering the following questionnaires:

- Modified socio-demographic survey (assess for any changes in housing, income)
- Modified ASI – follow-up (assesses for drug use)
- Behavioral risk questionnaire (assesses injection behaviors)
- AUDIT-C (assesses alcohol use)
- Substance Use Treatment (assess past and present experience with treatment)
- PHQ-9 (assesses for depression)
- GAD-7 (assesses for anxiety)
- EQ-5D with added pain question (assesses quality of life)
- Shame Scale (assesses for shame associated with HCV infection)
- Medical Outcomes Social Support Scale (assesses for social support)

Collect the following samples:

- Urine for POC drug screening
- Collect 20 mL of whole blood in EDTA tubes to send to Quest Diagnostics for HCV viremia testing and for archiving.

Provide the following services:

- Counseling on avoidance of HCV transmission and HIV infection.
- Information on drug treatment and needle exchange programs, and other referrals as needed

The original HERO protocol involved a total of 13 research visits over a 30-month period. On May 2019, participants were offered the opportunity to participate in an extended follow-up period involving 4 additional research visits over a 12-month period. Participants were invited to participate in the protocol extension period (12 months). Participants were informed of all the procedures in the additional 4 visits. Only

participants who agreed to participate and signed the informed consent were enrolled in the additional visits.

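### Protocol 11.11 analyses reinfection as a proportion and by logistic regression, without time at risk, although testing after week 120 was opt-in and section 3.2 promises incidence and time-to-event analyses

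*Protocol*

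**What the plan says.** Protocol 11.11 is the only detailed plan for reinfection; the SAP covers SVR, treatment initiation, completion and adherence. For the estimate, 11.11 states: "The precision of proportion of participants who develop resistance or reinfection will be determined with 95% confidence intervals (CIs) calculated using exact binomial methods". For factors it states: "To identify factors associated with resistance or reinfection, we will conduct bivariate analysis using (exact) logistic regressions". A multivariable logistic model then takes the factors significant at 0.05. No time origin, person-time, censoring or horizon is given.

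Section 3.2 (Secondary Objective 1) is broader. The objective reads "Reinfection: whether (a) rate (incidence), and the (b) proportion who become reinfected with HCV is higher in the PN arm", and the same section adds: "We will also conduct time to event analyses to examine drug resistance and reinfection outcomes".

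Follow-up is described under Visit 13 (8.6.9): "The original HERO protocol involved a total of 13 research visits over a 30-month period". Four further visits (weeks 132, 144, 156 and 168) were offered from May 2019, and only "participants who agreed to participate and signed the informed consent were enrolled in the additional visits". The documents do not give the share who agreed. Section 11.7 bases primary analyses on available data without imputation. It does not say how to code a participant who has incomplete follow-up and no detected reinfection.

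**The concern.** Reinfection can be seen only when RNA is tested. SVR12 is at week 24, so planned testing after SVR12 lasts 96 weeks for a participant who declined the extension and 144 weeks for one who joined it. A yes/no outcome does not carry that difference. If everyone without a detected reinfection is coded as no, untested time is treated as reinfection-free.

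Two results are exposed:

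- **The proportion reinfected.** It refers to no defined period and cannot be set beside the per-person-year rates quoted in section 2.1, where the protocol notes how little is known about reinfection in the DAA era.
- **The factor analysis under Secondary Objective 2.** Section 2.1 lists unstable housing, incarceration and ongoing substance use as things that impede stability. Such factors could plausibly relate both to reinfection and to staying in follow-up.

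**Working it through.** **The plan's own figures.** With 27 reinfections in 540 (5%), the Wilson 95% interval is 3.46% to 7.18%, which matches the stated 3.5% to 7.2%. The exact method that 11.11 names gives 3.3% to 7.2%, a small difference. For a factor at 2.5% vs 7.8%, the odds ratio is (0.078/0.922)/(0.025/0.975) = 3.30, as stated. Power with 270 per group at two-sided 0.05 is 79.7%, against a stated figure above 80%. These figures reproduce, but none has a time span attached.

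**Inputs for the check.**
- From the documents: 96 weeks = 96×7/365.25 = 1.84 years; 144 weeks = 2.76 years; reinfection rates from section 2.1, "5.2/100 person years (py) for those who report injection drug use after treatment, and less (3.2/100 py".
- Assumed: constant hazard, no other loss to follow-up, ever/never coding, and the opt-in share e.

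**Formula.** Cumulative risk is F(T) = 1 − exp(−rate × T). The crude proportion is F(1.84) + e × [F(2.76) − F(1.84)].

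**Crude proportion at 5.2/100 PY.** F(1.84) = 9.12% and F(2.76) = 13.37%.

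| Opt-in share (assumed) | Crude proportion |
|---|---|
| 0% | 9.1% |
| 25% | 10.2% |
| 50% | 11.2% |
| 75% | 12.3% |
| 100% | 13.4% |

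The underlying rate is 5.2/100 PY in every row. At 8/100 PY, also cited in section 2.1, the two ends are 13.7% and 19.8%. The plan's own 5%, if it means 96 weeks, implies −ln(0.95)/1.84 = 2.79/100 PY and 7.4% by 144 weeks.

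**Factor odds ratios, unexposed group at 5.2/100 PY.**

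| Opt-in, unexposed / exposed (assumed) | No true effect | Hazard ratio 2 |
|---|---|---|
| 50% / 50% | 1.00 | 2.12 |
| 30% / 70% | 1.19 | 2.53 |
| 70% / 30% | 0.84 | 1.78 |
| 0% / 100% | 1.54 | 3.31 |

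For the null factor at 30%/70%, the proportions are 10.4% and 12.1%, so the odds ratio is (0.121/0.879)/(0.104/0.896) = 1.19. With full follow-up for all, a hazard ratio of 2 corresponds to an odds ratio of 2.15.

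**The protocol's two cited rates, injecting 5.2 vs not injecting 3.2/100 PY.** At 3.2/100 PY, F is 5.72% and 8.45%. The week-168 odds ratio is (0.1337/0.8663)/(0.0845/0.9155) = 1.67.
- Equal 50% opt-in: 11.25% vs 7.09%, odds ratio 1.66.
- Opt-in 40% among injectors, 80% among others: 10.82% vs 7.91%, odds ratio 1.41.
- Opt-in 80% among injectors, 40% among others: 12.52% vs 6.81%, odds ratio 1.96.

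A model that uses observed time would recover the rate and the hazard ratio in all these cases, provided censoring is non-informative given covariates.

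**The case against.** The strongest reply is section 3.2. The protocol does commit to an incidence rate and to time-to-event analysis of reinfection, so a reader who infers that only an ever/never analysis is intended goes too far. But that commitment sits under the by-arm objective, no section gives it a model, time origin or censoring rule, and 11.11 assigns the search for factors to logistic regression alone.

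A reader might also infer that decliners are coded as reinfection-free. That is the natural reading of a yes/no outcome, but it is not written. Section 11.7 leaves room for available-case exclusion. That would discard decliners' 96 observed weeks or, if earlier events were kept, select on the outcome. Some rule has to be stated either way.

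Finally, a reader might infer that the factor odds ratios are biased. The documents do not support this. Bias requires opt-in or retention to differ by the factor, no opt-in figures are given, and the direction is unknown. Smaller gaps also matter less. At 4.2/100 PY, a null factor gives 0.92 when opt-in is 40% (exposed) vs 60% (unexposed), and 0.96 at 45% vs 55%. With 270 per group and about 9.5% events, sampling error alone spans roughly a factor of 1.8 either side, and the plan claims power only for odds ratios above 3.3. This limits the size of the factor concern. It does not help the crude proportion, which lacks a time span even when opt-in is unrelated to every factor.

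**Conclusion.** The point holds as a mismatch within the protocol. The detailed reinfection plan ignores time at risk, while one third of the planned post-SVR12 testing (48 of 144 weeks) was optional, and the time-to-event work promised in section 3.2 is never specified.

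The effect on the crude proportion needs no differential opt-in: 9.1% to 13.4% at 5.2/100 PY, given ever/never coding, constant hazard and no other loss. The effect on factor odds ratios is conditional and can go either way: about 0.84 or 1.19 for a null factor at an assumed 30%/70% split, about 1.5 at the 0%/100% extreme, and none if opt-in and retention are equal. Only the secondary reinfection results are affected; the SVR comparison is not. The change should be made, because it is cheap and carries out what section 3.2 already promises.

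**What to change.** In 11.11, for reinfection only:

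1. Define the risk set as participants with SVR, the time origin as the SVR-defining RNA test, and censoring at the last RNA test.
2. Replace the logistic regressions for factors with a model that uses observed time at risk. Discrete-time complementary log-log by visit, Poisson regression with a person-time offset, or interval-censored survival would each serve. State the assumption of non-informative censoring given covariates.
3. Report incidence per 100 person-years, and the cumulative proportion at week 120 by Kaplan-Meier or life table. Report week 168 separately for the extension.

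Logistic regression restricted to participants tested to week 120 is not an adequate substitute. It would drop those reinfected earlier and then lost, which selects on the outcome.

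The cost is wording plus standard procedures on RNA results already scheduled every 12 weeks. The week-120 summary sets later events aside, but the hazard model still uses them. The precision statement should be redone for the smaller risk set: 540 × 0.80 = 432 to 540 × 0.89 = 481 participants at the plan's SVR rates. For example, 23 of 456 gives an exact interval of 3.2% to 7.5%.
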